## 1.0 Background and Rationale

Schizophrenia is a chronic and disabling illness that is associated with impairments in independent living as well as social and vocational functioning. Schizophrenia also represents an important societal burden; only 10% of individuals maintain employment, translating into annual lost wages of nearly \$15 billion. Cognitive dysfunction is a core facet of schizophrenia, contributing to profound social and vocational difficulties. Episodic memory (EM) is an important cognitive domain that is commonly impaired in schizophrenia.

EM combines event-specific autobiographical experiences and information regarding the context in which events took place, aiding in making decisions and guiding actions in the present. EM deficits are associated with poor insight, poor treatment compliance, and significant social and occupational dysfunction. There are no effective treatments for EM impairment, due in large part to a gap in knowledge regarding the neural mechanisms of EM dysfunction. In light of the significant functional disability and poor outcomes associated with deficits in EM there is a critical need for more effective therapeutic options for this important cognitive deficit.

Recently research has identified that dysconnectivity in key EM structures, such as the precuneus, may be associated with EM impairment, though the precise role of disordered cortical circuitry remains elusive. The precuneus is believed necessary for autobiographical and episodic memory retrieval and mentalizing. Cabeza et al. (2008) suggested that the precuneus is involved in supporting retrieval search, monitoring, and verification. Altered function in the precuneus could be related to deficient EM functioning in various ways, including an impaired ability to make accurate assessments of familiarity. Disrupted precuneus function may also impair attentional networks, interfering with the ability to retrieve previously encoded information. The precuneus has reciprocal connections with other brain regions, including EM relevant structures such as the dorsolateral prefrontal cortex (DLPFC), the anterior cingulate cortex (ACC), and the hippocampus. Previous studies, including our own, have demonstrated that altered precuneus activity is associated with EM deficits in schizophrenia. However, relative to other structures, the specific role of the precuneus in cognitive dysfunction in schizophrenia has not yet been determined. Clearly defining the role of structures, such as the precuneus, in EM dysfunction will enable investigators to develop more targeted therapeutic interventions for this important clinical phenomenon.

Repetitive transcranial magnetic stimulation (rTMS) is a non-invasive neuromodulation technique that received FDA clearance for use in treatment resistant major depressive disorder in 2008 and has become commonly used in clinical practice. rTMS utilizes the application of a repetitively pulsed magnetic field over the scalp to induce an electric field within a discrete area of the cerebral cortex. This electric field results in altered ion flow across the neuronal cellular membrane and ultimately changes in neuronal polarization. rTMS modulates cortical activation depending on the stimulation parameters used. Physiological studies have provided evidence that low-frequency (LF) rTMS produces an inhibitory effect on local cortical excitability. In contrast, evidence suggests that high-frequency (HF) rTMS produces an increase in local cortical excitability. Studies have also demonstrated that rTMS may increase or decrease functional connectivity between separate but related cortical structures, utilizing high and low frequency stimulation, respectively.

Work by our group and others have shown that rTMS is a viable option for investigating cognitive dysfunction in schizophrenia. We recently completed a pilot-study investigating the effects of HF rTMS, compared to sham stimulation, on cognitive dysfunction in an early

phase psychosis (EPP) population. This study administered bilateral, sequential, double-blinded sham stimulation or HF (20 Hz) rTMS targeting the DLPFCs in twenty subjects with EPP. Ten sessions of rTMS or sham were administered over the course of two-weeks. Our pilot-study demonstrated not only a beneficial effect of rTMS on cognition but also that the intervention is safe and well tolerated in subjects with EPP. There were no significant adverse events during the course of this study and there were no significant differences in adverse events between the rTMS and sham group.

In spite of existing work studying rTMS as a treatment modality in schizophrenia, there are no studies that have examined the effects of precuneus directed rTMS on either EM deficits or the neurocircuitry subserving EM in schizophrenia. It is also important to note that the vast majority of studies using rTMS in schizophrenia have examined chronic populations where confounds associated with prolonged duration of illness may be present. EPP is a desirable population to study because these individuals tend to have fewer psychiatric and physical comorbidities and less antipsychotic drug exposure, all of which are factors that may confound investigations of new treatment interventions for this illness. In light of the significant unmet medical need associated with schizophrenia and the grave clinical effect of disrupted EM in the illness, rTMS modulating the precuneus, and potentially EM circuitry, represents an unexplored and potentially novel potential treatment option.

This study proposes to combine functional magnetic resonance imaging (fMRI) with inhibitory LF (1 Hz) and excitatory HF (20 Hz) rTMS protocols to interrogate the effects of rTMS targeting the precuneus on: 1) precuneus activation during EM task performance; 2) functional connectivity between the precuneus and key EM circuitry, specifically the DLPFC, ACC, and hippocampus and 3) performance during an in-scanner scene encoding and recognition EM task. This study will provide vital preliminary data on target engagement informing future clinical trials seeking to utilize rTMS to treat EM impairment in schizophrenia. This is an important population for study because if effective, rTMS may represent a novel treatment for EM deficits in schizophrenia. This study will also seek to refine the understanding of the brain circuitry that mediates the potential pro-EM effects of rTMS through the use of fMRI at baseline and following the course of rTMS administration.

[figure not shown]
## 2.0 Specific Aims and Hypothesis

The **first primary aim** is to demonstrate how targeting the precuneus with rTMS impacts functional activation (FA) in individuals with schizophrenia during EM tasks. We predict that, compared to sham stimulation, 1 Hz rTMS will result in decreased FA of the precuneus and 20 Hz rTMS will result in increased FA of the precuneus. The **second primary aim** is to demonstrate how targeting the precuneus with rTMS impacts precuneus functional connectivity (FC) in individuals with schizophrenia. We predict that compared to sham stimulation, FC between the precuneus, the DLPFC, the hippocampus, and the ACC will be decreased in response to 1 Hz rTMS and increased in response to 20 Hz rTMS. The **third primary aim** is to characterize the relationships between EM performance and changes in precuneus functional activation and connectivity. We predict that improved EM performance will be associated with increased precuneus functional activation and connectivity, while poorer EM performance will be associated with decreased precuneus functional activation and connectivity. The **secondary aim** is to characterize how targeting the precuneus with rTMS affects episodic memory performance in individuals with schizophrenia. We predict that compared to sham stimulation, 1 Hz rTMS will impair EM performance and that 20 Hz rTMS will improve EM performance.

### 3.0 Study Design

This will be a single site pilot study. 30 subjects with EPP, defined as medical record documentation of the onset of clinically significant psychotic symptoms within the past ten years, will be enrolled. Prior to randomization (Session 1), subjects will undergo fMRI during EM and RS paradigms. This baseline scan will also include a high-resolution structural sequence for neuronavigation purposes. Then on three separate days each occurring one-week apart, subjects will receive one session of inhibitory (1 Hz) rTMS, one session of excitatory (20 Hz) rTMS, and one sham stimulation session targeting the precuneus. The order of the three interventions will be randomized. Immediately following each rTMS or sham session, subjects will undergo repeat fMRI during EM and RS paradigms. We will also examine the effect of rTMS on EM performance.

**Fig 1. Study Outline**

#### *rTMS Set up and Administration*

rTMS will be delivered using the Magventure MagPro X100 Magnetic Stimulator (Magventure Inc., Alpharetta, Georgia). Motor threshold (MT) will be determined using single pulse stimulation over the left primary motor cortex, assessed as the lowest intensity producing five visible movements of the right abductor pollicis brevis out of ten stimulations. The Magventure MagPro X100 is equipped with a research-dedicated coil with combined active and sham stimulation capabilities. The active and sham functions share the same acoustic properties and sham mimics cutaneous stimulation, facilitating double-blinding. Study conditions (20 Hz, 1 Hz, sham) will be assigned a label, such as A, B, or C, by a non-blinded staff member who is not directly involved with the research team. Subjects will be assigned a sequence of blinded study conditions in randomized and counterbalanced fashion.

**High Frequency rTMS:** High frequency rTMS, or rTMS greater than 5 Hz, leads to facilitatory effects on brain excitability. Previous studies have demonstrated that administration of as little as a single train or a small number of trains are able to produce an immediate increase in cortical excitability. Additionally, earlier investigations have utilized high frequency rTMS in schizophrenia populations, demonstrating that the treatment is safe, well-tolerated and capable of altering cognitive performance. Our group has employed 20 Hz rTMS at 110% of motor threshold in a stimulation protocol in-line with the current proposal to improve cognitive function in an EPP cohort. **High Frequency rTMS Protocol:** Subjects will receive one session of high frequency rTMS within the following stimulation parameters: 20 Hz, at 120% of MT, 60 trains (1.0 second per train), 20 pulses per train, inter-train interval of 15 seconds, for a total of 1200 pulses over 16 minutes.

**Low Frequency rTMS:** Low frequency rTMS, or rTMS at 1 Hz or less, is able to produce an inhibitory effect on local brain activity. This has been observed in healthy subject motor corticospinal output. Previous studies have demonstrated that a single session of 1 Hz rTMS is capable of inhibiting local brain activity and modulating distal but related circuitry. This work is in-line with the use of 1 Hz stimulation proposed in this study. **Low Frequency rTMS Protocol:** Subjects will receive one session of low frequency rTMS within the following stimulation parameters: Continuous 20-minute train of 1 Hz rTMS, at 120% of MT, for a total of 1200 pulses. This protocol was shown by Chen et al. (2013) to produce an inhibitory effect on local cortical excitability as well as effects on connectivity of related circuitry.

Both high and low frequency stimulation protocols are within safety limits for rTMS.

### *Neuronavigation*

Brainsight software (Rogue Research, Montreal Canada) will be used to reliably target the precuneus for stimulation. First, the subject's individual anatomy will be registered stereotactically using the acquired structural MPRAGE brain image and fiduciary points on the scalp visible with a Polaris vicar camera (Brainsight software). We will use the center of mass of the precuneus (derived via Freesurfer parcellation; Destrieux Atlas; left/right combined) to identify the specific coordinates for stimulation. Stimulation site will be marked on a swim cap worn by the subjects at each stimulation session, consistent with prior TMS studies.

**Electrical field modeling:** The processed structural image will be used to generate E-fields based on realistic conductor head models using SimNIBS (2.1 or latest version). SimNIBS includes volume conductor modeling (following FreeSurfer segmentation), TMS coil specific magnetic dipole estimations, and finite element modeling of the electric field at each tetrahedral element of the subject's head mesh. In anticipation of actual TMS sessions with each patient, we will find the optimal TMS positioning to most strongly influence the precuneus, which will be the target for neuronavigated rTMS delivery.

### *rTMS administration monitoring*

All subjects will be instructed to wear earplugs during each rTMS session and will be monitored by medically trained research staff throughout the entirety of each rTMS session.

### *Duration of Treatment*

Subjects will complete three stimulation sessions (HF, LF, and sham) over three weeks, with one session occurring each week. Previous work has demonstrated that a single session of rTMS is sufficient to modulate target site functional activation as well as functional connectivity between the stimulation target and associated circuitry.

[figure not shown]
### *Sample Size*

We plan to enroll 30 subjects and anticipate a 20% drop out rate, yielding 24 completers. This is consistent with our previous clinical trial efforts, including a study of adjunct rTMS for cognitive impairment. For all planned analyses, a total of 24 subjects in a cross-over design will result in 0.8 power to detect an assumed treatment difference at medium effect size 0.6; using an alpha level of 0.05 and conservatively assumed a within-subject correlation of 0.5. As no precuneus rTMS pilot data was available, this standardized effect size of 0.6 is considered a conservative estimate to detect significant results.

### *Clinical Research Site*

The IU Psychotic Disorders Program (IUPDP), which is directed by [name] and is part of the IU Department of Psychiatry, is located in Indianapolis, Indiana. IUPDP research personnel will manage the day-to-day activities of conducting the trial, including subject recruitment, consenting and screening subjects, conducting study visits, and performing assessments. The IUPDP has 2 research psychiatrists, a fully dedicated study manager, a fully dedicated study coordinator, one dedicated subject recruiter, one dedicated research technician, and two raters (1 PhD, 1 Masters level) who have been trained and have extensive experience in conducting the assessments and cognitive tests used as outcome measures.

**Fig. 2 E-field precuneus modeling**

## 4.0 Study Population (Inclusion/Exclusion Criteria)

### Inclusion criteria:

1. Between 18 and 40 years of age
2. Within 10.5 years (10 years, 6 months) of illness onset as defined by entry into treatment for psychotic symptoms
3. Able to give informed consent
4. Willing and able to adhere to the study schedule
5. Structured Clinical Interview for DSM-5 (SCID-5) diagnosis of schizophrenia
6. Clinical stability defined by:
  - a. Subjects must not have experienced an exacerbation of their illness within 4 weeks prior to randomization, leading to an intensification of psychiatric care in the opinion of the investigator. Examples of intensification of care include, but are not limited to: inpatient hospitalization, day/partial hospitalization, outpatient crisis management, or psychiatric treatment in an emergency room AND
  - b. Antipsychotic treatment stability for at least 4 weeks prior to randomization (no change in antipsychotic dosing or addition of new antipsychotic medication)

### Exclusion criteria:

1. Lifetime history of a seizure, excluding febrile seizures and those induced by substance withdrawal
2. First degree relative with idiopathic epilepsy or other seizure disorder
3. History of significant neurological illness
4. History of head trauma as defined by a loss of consciousness or a post-concussive syndrome
5. Pregnant or breast feeding
6. Known IQ < 70 based on subject report
7. Current acute, serious, or unstable medical conditions
8. Metallic objects planted in or near the head, including implanted pacemaker, medication pump, vagal stimulator, deep brain stimulator, TENS unit, ventriculoperitoneal shunt, or cochlear implants
9. Contraindications to MRI or otherwise unable to tolerate MRI procedures
10. History of electroconvulsive therapy
11. Subjects taking clozapine
12. Subjects who have participated in a clinical trial with any pharmacological treatment intervention for which they received study-related medication in the 4 weeks prior to randomization
13. Subjects considered a high risk for suicidal acts – active suicidal ideation as determined by clinical interview OR any suicide attempt in 90 days prior to screening
14. Current DSM-5 diagnosis of alcohol or drug use disorder (excluding nicotine or caffeine)
15. Subjects who require concomitant treatment with prohibited medication, as specified in Attachment 2

## **5.0 Subject Recruitment**

Subjects will be recruited through referring community mental health centers, treatment providers, the IUPDP registry, and self-referrals through advertisement and word-of-mouth.

## **6.0 Clinical Assessments and Procedures**

The following assessments will be administered according to the Study Procedures Table (Attachment 1). All assessments will be completed by study personnel trained to administer the instruments and will be based on interviews with the subject or questionnaires completed by the subject.

### *Columbia Suicide Severity Rating Scale (C-SSRS)*

The C-SSRS captures the occurrence, severity, and frequency of suicide-related thoughts and behaviors during the assessment period. The definition of behavioral suicidal events used in this scale is based on those used in the Columbia Suicide History Form^45. During the baseline assessment, questions are in relation to lifetime experiences and all subsequent questioning is in relation to the last assessment.

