#### *Statistical Analyses*

[figure not shown]
Intent-to-treat (ITT) analysis will be conducted, and thus all randomized subjects will be included. ITT is the most conservative approach for detecting a treatment effect, because the inclusion of subjects who do not complete the intervention will serve to underestimate rather than overestimate any treatment effect. Sensitivity analyses including a subset analysis using a “completers only” analysis will be performed to test the robustness of the findings. Statistical tests will be performed based on two-sided test at the 5% level of significance.

Descriptive characteristics at baseline will be summarized for the whole sample. For continuous variables, the mean and standard deviation will be presented. For categorical variables, the number and percent will be reported.

Primary analyses: For each subject, change scores in activation of the precuneus (aim 1), functional connectivity (aim 2), and EM performance (aim 3) will be calculated at each treatment by using (post - baseline). We will employ a mixed model for repeated measures ANCOVA, of the general form for each measure:  $change_{ijk} = \mu + \alpha_i + b_{ij} + \gamma_k + \beta X_{ijk} + \tau_d(i, k) + e_{ijk}$ , where  $\mu$  is overall mean;  $\alpha_i$  is the effect of the  $i$ th treatment sequence ( $i = 1, 2, \dots, 6$ );  $b_{ij}$  is the random effect with variance  $\sigma_b^2$  for the  $j$ th subject ( $j = 1, 2, \dots, 24$ ) of the  $i$ th treatment sequence;  $\gamma_k$  is the period effect ( $k = 1, 2, 3$ );  $\beta X$  is the baseline value;  $\tau_d(i, k)$  is the direct effect of the treatment administered in period  $k$  of sequence group  $i$ ; and  $e_{ijk}$  is the random error with variance  $\sigma^2$  for the subject in period  $k$ . Based on this model, we will compare the treatment difference in change score between 1 Hz and Sham as well as 20 Hz and Sham. Under the assumption of missing at random, this mixed effect model will provide the unbiased estimates.

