## ATTACHMENT 1: Study Procedures Table

Visit Number	1 c	2	3	4	5 d
Day b		0	7	14	28
Informed Consent	X				
Screening (Demographics, Inc/Exc, Medical & Psychiatric History of Self and Family)	X				
SCID V a	X				
Physical Exam	X				
CGI-S	X	X	X	X	
CGI-I		X	X	X	
Vitals	X	X	X	X	
Urine Drug Screen	X				
Pregnancy Test	X	X	X	X	
Motor Threshold Determination	X				
MRI – Baseline & Baseline EM Task	X				
Randomization (Order of Study Intervention)		X			
Neuro Navigation		X	X	X	
rTMS/sham Administration		X	X	X	
Post Stimulation MRI-EM Task		X	X	X	
PANSS	X				
AIMS	X	X	X	X	
C-SSRS	X	X	X	X	
Adverse Events	X	X	X	X	X
Concomitant Medication	X	X	X	X	X
a If subject received a SCID interview within 6 months of screening, it may not be repeated at the discretion of the PI					
b Ideal time frame for administration will be on each Monday of three consecutive weeks. A total of 3 sessions. Visit window deviations will be granted at the discretion of the PI and will not be a protocol violation.					
c Visit window for Visit 1 is 0-30 days					
d Visit 5 may occur by phone and ideally will occur 14 days after Visit 4. Visit window deviations will be granted at the discretion of the PI and will not be a protocol violation.					

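### No C-SSRS is scheduled after the third stimulation session; only general adverse event and concomitant medication collection covers the 14 days that follow

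*Combined protocol and SAP*

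**What the plan says.** Section 6.0 ties the timing of the clinical scales to the schedule table: "The following assessments will be administered according to the Study Procedures Table (Attachment 1". For the C-SSRS it then sets the recall period: "During the baseline assessment, questions are in relation to lifetime experiences and all subsequent questioning is in relation to the last assessment".

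In Attachment 1 the C-SSRS row is marked at Visits 1, 2, 3 and 4, and the Visit 5 cell is blank. Stimulation takes place at Visits 2, 3 and 4 (Days 0, 7 and 14): "rTMS/sham Administration X X X". Visit 5 falls on Day 28, and footnote d describes it: "Visit 5 may occur by phone and ideally will occur 14 days after Visit 4". Two rows are marked at Visit 5, adverse events ("Adverse Events X X X X X") and concomitant medication.

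Which condition comes third varies between subjects. Section 3.0 states: "The order of the three interventions will be randomized". Its paragraph on rTMS set-up adds: "Subjects will be assigned a sequence of blinded study conditions in randomized and counterbalanced fashion". The documents do not say whether the C-SSRS comes before or after stimulation within Visits 2 to 4.

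**The concern.** A since-last-assessment instrument reports on an exposure only if it is given again later. Sessions 1 and 2 get that later administration and session 3 does not, although a contact two weeks after session 3 is already planned.

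The plan itself treats suicidality as something to measure in a structured way. Exclusion criterion 13 screens for it, and the C-SSRS is given at each of Visits 1 to 4. No reason is given why the first two sessions warrant a structured look-back and the third does not. At stake is whether suicidal thoughts or behaviour arising after the last session are asked about with the chosen instrument, or are recorded only if they surface through general adverse event collection.

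**Working it through.** **Inputs.** From Attachment 1: stimulation on Days 0, 7 and 14; C-SSRS at screening and on Days 0, 7 and 14; adverse events at all five visits, the last on Day 28. From Section 3.0 (Sample Size): 30 enrolled, 20% dropout, 24 completers. From Section 13.0: six treatment sequences in the model. Visit days are the ideal ones; the footnotes leave deviations to the PI.

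**Plan's own figures.** Visit 5 minus Visit 4 = 28 − 14 = 14 days, which agrees with footnote d. Completers = 30 × (1 − 0.20) = 24, which agrees with Section 3.0.

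**Follow-up after each session, in days.**

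| Session (day) | To next C-SSRS | To last C-SSRS | To last adverse event contact |
|---|---|---|---|
| 1 (Day 0) | 7 − 0 = 7 | 14 − 0 = 14 | 28 − 0 = 28 |
| 2 (Day 7) | 14 − 7 = 7 | 14 − 7 = 7 | 28 − 7 = 21 |
| 3 (Day 14) | none | 0 | 28 − 14 = 14 |

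From the first stimulation to the last contact is 28 days. C-SSRS look-back covers Days 0 to 14, so 14/28 = 50%. Adverse event collection covers all 28.

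**Sessions affected.** 24 completers × 3 sessions = 72. Third sessions = 24, and 24/72 = 33%.

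**By condition.** Three conditions give 3! = 6 orders, and each condition is last in 2 of the 6. With equal numbers per sequence, 24 × 2/6 = 8 completers have a given condition last, so 8 + 8 = 16 of 24 have an active condition last. Equal filling is an assumption; the protocol says counterbalanced but gives no numbers per sequence.

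**Order within the visit.** There are two cases.

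- *C-SSRS before stimulation:* Visit 2 covers screening to Day 0 and contains no exposure, Visit 3 follows session 1 and Visit 4 follows session 2. Nothing reaches session 3.
- *C-SSRS after stimulation:* Visit 4 picks up the remaining part of that visit after session 3, and no more. In this case the Visit 3 and Visit 4 look-backs also mix the week after one session with the hours after the next.

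Neither order gives session 3 C-SSRS coverage beyond its own day.

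**With the C-SSRS added at Visit 5.** Look-back after session 3 rises from 0 to 28 − 14 = 14 days, and overall coverage from 14 to 28 of 28 days. No sample size or power figure changes.

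**The case against.** The strongest reply is that session 3 is followed up. Visit 5 collects adverse events and concomitant medication 14 days later. Section 10.0 has adverse events followed until they return to baseline or stabilise, and Section 12.0 sends unanticipated events to the PI at once. A suicidal event, or an exacerbation that changed treatment, could be recorded by these routes. This stands. A reader might infer from the schedule that third sessions have no suicidality follow-up at all, and the documents do not support that. What is missing is the structured instrument. Section 10.0 specifies no method for asking about suicidality, so the two are not equivalent.

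A second reply is that Section 13.0 plans no comparison of C-SSRS or CGI by condition; its analyses concern activation, connectivity, memory performance and mediation. This also stands. It would be wrong to infer that every safety statement by condition rests on periods 1 and 2, because adverse event data reach all three.

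A third reply is that a C-SSRS at Visits 3 and 4 can inform whether the next session goes ahead, while one at Visit 5 cannot, and that the population is clinically stable with high suicide risk excluded at entry. Ending the scale with the last exposure is therefore a coherent choice, and Section 6.0 and Attachment 1 do not contradict each other. That makes this an improvement and not the correction of an error. It does not explain why a look-back scale should omit the last exposure when a later contact already exists.

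**Conclusion.** The point holds in a limited form. No scheduled C-SSRS follows the third session, and general adverse event and concomitant medication collection alone covers the following 14 days. This concerns 24 of 72 sessions among the planned completers (33%), about 8 per condition.

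The count of 24 rests on the planned completers. The split by condition rests on equally filled sequences. The day counts rest on the ideal visit schedule. The finding does not depend on whether the C-SSRS precedes or follows stimulation, and it does not rest on any view of how often ideation goes unreported, on which the documents are silent.

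The gap concerns the completeness of safety ascertainment. The primary analyses, the mediation analyses and the power are unaffected. The CGI scales and the AIMS also end at Visit 4, but the point does not need them.

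**What to change.** In Attachment 1, mark the C-SSRS (since-last-assessment form) at Visit 5, in person or by phone as footnote d already allows. In Section 6.0 or as a table footnote, state that at Visits 2 to 4 the C-SSRS is given before stimulation, so that the Visit 3, 4 and 5 look-backs follow sessions 1, 2 and 3 respectively.

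The cost is one edit to the schedule, one sentence of text and a few more minutes at an existing contact, with no new visit and no added staff. One limitation remains: the look-back after session 3 would be 14 days against 7 for sessions 1 and 2, so any descriptive listing by session should show the interval length. Adding the CGI scales at Visit 5 is optional.
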